3.2.1.2 Tolvaptan Conventional Tablet

One tolvaptan conventional tablet 15 mg or 30 mg will be administered with about 150 mL of water under fasting conditions.

Both formulations will be administered after at least 10 hours of fasting. Subjects will not be allowed to eat until 4 hours postdose. Fluid intake will not be allowed from 2 hours before to 2 hours after dosing, excluding water given to swallow the tablet.

3.2.2 Treatment Period

After single oral dosing in Period 1, there is a 72-hour washout period, followed by single oral dosing in Period 2 (different from the formulation + regimen combination in Period 1). After single oral dosing in Period 2, there is a 72-hour washout period, followed by single oral dosing in Period 3 (different from the formulation + regimen combination in Periods 1 and 2).

3.3 Trial Population

A total of 84 healthy adult male subjects at least 20 years and less than 40 years of age will be enrolled.

Any enrolled subject who withdraws consent or is judged not to be able to receive IMP before the start of IMP administration will be replaced with a reserve subject.

Neither subject enrollment nor replacement will take place for subjects who are withdrawn from the trial after randomization.

3.4 Handling of Time Points

Data measured at the time points specified in the protocol will be used. Examinations specified for discontinuation and unscheduled examinations will be presented in lists, but will not be used in summaries.

4 Sample Size

With reference to the Guidelines for Bioequivalence Studies of Generic Products,¹ the sample size for this study was calculated as the number of subjects required to demonstrate that the 90% confidence intervals of the geometric mean ratios of the AUC_t and C_{max} of tolvaptan (OD tablet without water vs conventional tablet and OD tablet with water vs conventional tablet) fall inside the bioequivalence range of $\ln(0.8)$ to $\ln(1.25)$.

Of the prior crossover studies of tolvaptan in healthy adults, Study 156-00-002 reported the largest intra-individual variability (AUC_t and C_{max} , 0.033 and 0.056, respectively). Sample size calculation was performed using the method proposed by Diletti, et al. (1991)² based on the C_{max} , in which intra-individual variability was large.

When the ratio of the expected C_{max} with the tolvaptan OD tablet (administered with or without water) to that with the tolvaptan conventional tablet is assumed to be 1.05, at least 12 subjects per group are required to achieve a power of at least 90%. To account for withdrawals and dropouts, the sample size for this study was set to 14 subjects per group for 1 cohort, for a total of 42 subjects.

5 Statistical Analysis Sets

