- Plasma AVP concentration increased after dosing and remained high at 24 hours postdose. Serum sodium concentration increased after dosing but remained within normal physiological limits. No notable change was observed in serum potassium concentration.
- Fluid balance showed a negative value in the interval of 0 to 2 hours in a dose-dependent manner but showed gains from Day 2.

3) Safety Results

- The incidence of adverse events in the study was 50.0% (21/42 subjects) in the OPC-41061 groups and 14.3% (2/14 subjects) in the placebo group. The incidence of adverse events at least possibly related to the investigational medicinal products (= adverse drug reactions [ADRs]) was 45.2% (19/42 subjects) and 7.1% (1/14 subjects), respectively.
- By dose, the incidence of adverse events (in the descending order) was 100% (6/6 subjects) in the 120 mg and 90 mg groups, 41.7% (5/12 subjects) in the 30 mg group, and 33.3% (2/6 subjects) in the 15 mg, 45 mg, and placebo groups. No adverse event was reported in the 60 mg group.
- Frequent adverse events ($\geq 5\%$ incidence) in the OPC-41061 groups were “thirst” (8 subjects), “nasopharyngitis” (4 subjects), and “blood osmolarity increased,” “blood uric acid increased,” and “headache NOS” (3 subjects each).
- Serious adverse events (“sinus arrest” and “bradycardia NOS”) occurred in 1 subject in the 30 mg group. A causal relationship between these events and OPC-41061 could not be ruled out, but both events resolved without intervention.
- On laboratory values, no clinically significant variations were seen in any group including the placebo group.
- On vital signs (blood pressure, pulse rate, and body temperature), no clinically significant changes were seen excluding the serious adverse events reported in the 30 mg group. Body weight decreased after dosing in all groups. The decrease was larger in the OPC-41061 groups than in the placebo group. The mean decrease in 24 hours after dosing was 1.42 to 2.20 kg in the OPC-41061 groups and 0.89 kg in the placebo group.
- On electrocardiogram (ECG) findings, 1 subject in the 30 mg group experienced serious adverse events (“sinus arrest” and “bradycardia NOS”). Two subjects in the 90 mg group also had tachycardia (mild). These changes were judged to be “abnormal.” However, they were transient changes and resolved without intervention.

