3.7.1.6 At Discontinuation

Each subject who is withdrawn from the trial after IMP administration in Period 1 will undergo the observations, tests, and examinations shown in the table below. No all of the

Protocol 156-102-00136

procedures are to be mandatory if not feasible (eg, when the subject refuses to undergo the procedures specified for discontinuation or there is a medical emergency affecting the subject at that time). Also, the same procedures the subject has undergone on the day of trial discontinuation may be omitted.

Observations, Tests, and Examinations	Time Point(s) and Acceptable Time Window
Body weight	At discontinuation
Physical examination	
Vital signs (body temperature, blood pressure, pulse rate)	
Clinical laboratory test (blood and urine collection)	
12-lead ECG	
Adverse events	
Concomitant medications/therapy and restricted foods specified in Restrictions	

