Clinical Laboratory Test Value Changes: It is the investigator’s responsibility to review the results of all laboratory tests as they become available. This review will be documented by the investigator’s dated signature on the laboratory report. For each abnormal laboratory test result, the investigator needs to ascertain if this is an abnormal (ie, clinically significant) change from baseline for that individual subject. This determination, however, does not necessarily need to be made the first time an abnormal value is observed. The investigator may repeat the laboratory test or request additional tests to verify the results of the original laboratory tests. If this laboratory value is considered medically relevant by the investigator (subject is symptomatic, requiring corrective treatment or further evaluation), or if the laboratory value leads to discontinuation, and/or fulfills a seriousness criterion, this is considered an AE.

Severity: Adverse events will be graded on a 3-point scale and reported as indicated on the CRF. The intensity of an adverse experience is defined as follows:

1 = Mild: Discomfort noticed, but no disruption to daily activity.

2 = Moderate: Discomfort sufficient to reduce or affect normal daily activity.

3 = Severe: Inability to work or perform normal daily activity.

IMP Causality: Assessment of causal relationship of an AE to the use of the IMP is defined as follows:

Related: There is a reasonable possibility of a temporal and causal relationship between the IMP and the AE.

Not Related: There is no temporal or causal relationship between the IMP and the AE.

Protocol 156-102-00136

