7.6.4 Electrocardiogram Data

For each 12-lead ECG parameter, descriptive statistics of measurements and changes from baseline at each time point will be calculated. A shift table of ECG findings at each time point compared to baseline assessments will be created. Categorical analysis of corrected QT intervals (QTcF and QTcB) and their changes from baseline at each time point will be performed to calculate the number and percentage of subjects.

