8.5 Physical Examination

For each parameter, a shift table summarizing the findings at each time point compared to baseline will be created.

8.6 **Electrocardiogram Data**

For each 12-lead electrocardiogram (ECG) parameter, descriptive statistics of measurements and changes from baseline at each time point will be calculated. A shift table of ECG findings at each time point compared to baseline assessments will be created. For corrected QT intervals (QTcF and QTcB), the number and percentage of subjects meeting the following conditions will be calculated.

- Subjects with measurements “> 0.450 seconds,” “> 0.480 seconds,” and “> 0.500 seconds”
- Subjects with changes from baseline “> 0.030 seconds” and “> 0.060 seconds”

8.7 **Body Weight**

Descriptive statistics of measurements and changes from baseline at each time point will be calculated.

9 **Pharmacokinetic Analysis**

The following analyses will be performed for the bioequivalence analysis set per cohort. Sensitivity analysis of the primary variable will be performed on subjects for whom evaluable AUC_t and C_{max} values were obtained in Periods 1, 2, or 3.

9.1 **Statistical Analysis of Primary Variables**

- 1) For the AUC_t and C_{max} of tolvaptan, data will be log-transformed and analysis of variance (ANOVA) will be performed using group (group receiving conventional tablet first, group receiving OD tablet without water first, and group receiving tolvaptan OD tablet with water first), formulation and dosing regimen, subjects within group, and administration period (Period 1, Period 2, and Period 3) as factors. The analysis will use natural logarithms.

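### SAP 3.4 keeps unscheduled and discontinuation examinations out of every summary, so the SAP 8.6 QTc threshold counts can omit a qualifying post-dose reading that was recorded

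*SAP*

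**What the plan says.** SAP 3.4 sets the general rule on which data enter the tables: "Data measured at the time points specified in the protocol will be used". It continues: "Examinations specified for discontinuation and unscheduled examinations will be presented in lists, but will not be used in summaries".

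SAP 8.6 then asks for subject-level QTc counts: "For corrected QT intervals (QTcF and QTcB), the number and percentage of subjects meeting the following conditions will be calculated". The conditions are QTcF or QTcB above 0.450, 0.480 or 0.500 s, and a change from baseline above 0.030 or 0.060 s. No time basis is given. Protocol 7.6.4 does give one: "Categorical analysis of corrected QT intervals (QTcF and QTcB) and their changes from baseline at each time point will be performed". The ECG shift table in SAP 8.6 is also by time point: "A shift table of ECG findings at each time point compared to baseline assessments will be created". The laboratory shift table in SAP 8.3 is built the same way.

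The protocol expects off-schedule examinations. Section 3.7.1.6 says: "Each subject who is withdrawn from the trial after IMP administration in Period 1 will undergo the observations, tests, and examinations shown", and its table includes laboratory tests and a 12-lead ECG. Section 5.1 says of abnormal laboratory results: "The investigator may repeat the laboratory test or request additional tests to verify the results of the original laboratory tests".

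**The concern.** A mean at 24 h should use only 24 h readings. A count of subjects who crossed a QTc limit is different, because a reader may take it to mean at any time after dosing. Under SAP 3.4 it cannot mean that. The excluded examinations are more likely than scheduled ones to be prompted by a suspected abnormality, so leaving them out is not neutral.

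At stake is whether a zero in a safety table means that no such reading was recorded, or only that none was recorded at the scheduled visit. The plan does not tell the reader which.

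**Working it through.** The plan states no figure to reproduce here. The check sets the rules side by side and adds a small illustration of scale.

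**1. What is scheduled.** From Protocol 3.7.1.4.1, 3.7.1.4.5 and 3.7.1.5, each period has an ECG and a laboratory test before dosing and again at 24 h (±60 minutes), with none between.

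**2. How far 24 h is from peak exposure.** Protocol 3.7.3.1 gives a mean t_max of 2.18 to 3.21 h and a mean half-life of 3.33 to 4.39 h. The distance from mean peak to the 24 h examination, in half-lives, is (24 − t_max) / half-life:

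- shortest: (24 − 3.21) / 4.39 = 4.7
- longest: (24 − 2.18) / 3.33 = 6.6

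Any ECG or laboratory test made near the peak is therefore unscheduled, and SAP 3.4 keeps it out of the tables.

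**3. The two readings of SAP 8.6.** With only one scheduled post-dose ECG per period, a count at 24 h and a count over all scheduled post-dose ECGs are the same number. Stating the time basis alone changes nothing; the count changes only if off-schedule readings are admitted.

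**4. Where an off-schedule reading can still appear.**

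| Reading found only off schedule | Listing | QTc, ECG or laboratory table | TEAE table |
|---|---|---|---|
| Laboratory value that is medically relevant, leads to discontinuation or is serious (Protocol 5.1) | yes | no | yes |
| Other out-of-range laboratory value | yes | no | no |
| QTc over a threshold or abnormal ECG, judged an adverse event | yes | no | yes |
| QTc over a threshold or abnormal ECG, not judged an adverse event | yes | no | no |

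Rows two and four are the gap. An abnormal reading at a scheduled examination stays in the tables, including a scheduled laboratory value that prompts a repeat.

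**5. Scale.** The cohort size is 42 (SAP 4: 14 per group, 3 groups). Assume that all 42 receive a given treatment and that one subject crosses a QTc threshold only on an unscheduled or discontinuation ECG. Intervals are exact (Clopper-Pearson) 95%.

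- Under SAP 3.4: 0/42 = 0.0%. The upper limit is 1 − 0.025^(1/42) = 8.4%, so the interval is 0 to 8.4%.
- With an any-post-dose row: 1/42 = 2.4%. The lower limit is 1 − 0.975^(1/42) = 0.06% and the upper limit is 12.6%.

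If that subject left before the 24 h ECG and had no scheduled post-dose value, the scheduled result could instead be 0/41 (upper limit 8.6%).

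**6. Direction.** Adding valid post-dose readings to a count of subjects who ever exceeded a limit cannot reduce its numerator. The omission can only lower that count.

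**The case against.** The case for leaving the plan alone is substantial.

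- **The time-point tables are coherent.** An off-schedule reading has no cell in a table by scheduled time point. Protocol 7.6.4 defines the QTc categories by time point, so SAP 8.6 can be read as answering that question. This stands for the shift tables. For the QTc counts, the SAP sentence does not carry the basis over.
- **Nothing clinically relevant disappears.** Excluded examinations are listed, and SAP 8.2 tabulates TEAEs, including serious and related ones, without regard to examination schedule. This also stands, and it confines the gap to readings not judged adverse events.
- **Worst-value counts depend on testing frequency.** The trial is open-label and extra tests are at the investigator's discretion, so a subject tested more often has more chances to cross a limit. This stands, and is why the added rows belong beside the scheduled results and should not replace them.
- **No decision depends on these tables.** The objective is bioequivalence on AUC_t and C_max, and the safety analysis is descriptive.

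A reader might go further and infer that the tables omit the abnormal readings most likely to occur. The documents give no rate of abnormality by type of examination, so that cannot be shown.

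A reader might also cite Study 156-00-001, where sinus arrest and bradycardia "occurred in 1 subject in the 30 mg group" (Protocol 1.2.1). Those were rhythm events reported as serious adverse events. A repeat would appear in the serious TEAE table. The protocol reports no QTc prolongation with them and does not say whether they were found on or off schedule. One subject gives no sound basis for projecting omitted readings in Cohort 2. Nor is a discontinuation ECG assured: Protocol 3.7.1.6 allows procedures to be left undone when not feasible or already done that day.

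**Conclusion.** The point holds in a limited form. SAP 3.4 has no exception and nothing in SAP 8.3 or 8.6 brings the excluded readings back. A subject-level QTc count can therefore show zero when a qualifying post-dose reading was recorded, and some off-schedule laboratory and ECG abnormalities can appear only in listings.

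The illustrated size is one subject in 42, or 2.4 percentage points of a column. It assumes that all 42 subjects receive the treatment and that one qualifies only off schedule. The documents do not say how often that would happen. The tables by scheduled time point are not wrong, and the bioequivalence conclusions are unaffected. This is a cheap improvement to safety reporting.

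**What to change.** 1. **SAP 3.4:** limit the exclusion to summaries by scheduled time point.
2. **SAP 8.6:** state the time basis of the QTc threshold counts, and add an any-post-dose row for each threshold beside the scheduled-time-point result.
3. **SAP 8.3 and 8.6:** add one worst-post-dose shift table for laboratory values and one for ECG findings, also beside the scheduled results.
4. **Data for the additions:** use every reading after dosing and before the next period's dose, including unscheduled and discontinuation examinations. Attribute each to the formulation and regimen of that period, following the period rule that SAP 8.2 applies to TEAEs.

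The cost is a small amount of programming: one derived worst value per parameter, subject and period. No new data are needed. Counts may become slightly less favourable, and the added rows will depend to some extent on how often a subject was tested; a footnote should say so.

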5.1 Efficacy Analysis Set

No efficacy analysis will be performed in this trial.

5.2 Safety Analysis Set

The safety analysis set will include all subjects that were administered at least one dose of IMP.

5.3 Bioequivalence Analysis Set

The bioequivalence analysis set will include all subjects with both AUC_t and C_{max} values across Period 1, 2, and 3.

5.4 Handling of Missing Data

Missing values will not be imputed.

6 Primary and Reference Endpoint Variables

6.1 Primary Variables

AUC_t and C_{max} of tolvaptan

6.2 Reference Variables

- 1) Plasma concentration-time profile of tolvaptan
- 2) AUC_{∞} , MRT_{∞} , t_{max} , λ_z , $AUC\%$ Extrap, $t_{1/2, z}$, CL/F , $CL/F/BW$, and t_{last} of tolvaptan
- 3) By-subject ratios of AUC_t , C_{max} , AUC_{∞} , MRT_{∞} , and λ_z of tolvaptan for administration of OD tablet with and without water to those for administration of conventional tablet
- 4) Difference (value for OD tablet minus value for conventional tablet) in t_{max} by subject between administration of OD tablet without water and administration of conventional tablet and between administration of OD tablet with water and administration of conventional tablet

6.3 Subject Disposition

The number of screened subjects will be summarized. In each cohort, overall and for each group (the conventional tablet first group, OD tablet with water first group, and OD tablet without water first group), the number of randomized subjects, the number of subjects administered IMP, the number of completed subjects, and the number of

discontinued subjects will be summarized. The percentages of subjects with each reason for discontinuation relative to the number of randomized subjects will be summarized.

The numbers of subjects included in the bioequivalence analysis set and safety analysis set, and the percentages of these subjects relative to the number of randomized subjects, will be summarized for each cohort, overall, and for each group.

6.4 Demographic and Other Baseline Characteristics

For the bioequivalence analysis set and safety analysis set, descriptive statistics (number of subjects, mean, standard deviation, minimum, median, and maximum) of the age, height (cm), body weight at screening (kg), and BMI (kg/m^2) will be calculated in each cohort, overall and for each group. Distributions (numbers of subjects, %) of the history of smoking and history of alcohol consumption will be calculated.

6.5 Medical History

For the bioequivalence analysis set and safety analysis set, distributions for presence or absence of medical history and current symptoms will be calculated in each cohort, overall and for each group.

6.6 Investigational Medicinal Product Compliance

This will not be summarized in this trial.

6.7 Prior and Concomitant Medication

This will not be summarized in this trial.

6.8 Protocol Deviations

Distributions will be calculated for each type of significant deviation from the protocol in each cohort.

7 Efficacy Analysis

Not applicable.

8 Safety Analysis

Analysis will be performed by formulation and dosing regimen in each safety analysis set per cohort. Values obtained immediately before IMP administration in each period will be handled as baseline.

8.1 Extent of Exposure to Investigational Medicinal Product

The percentages of subjects administered IMP relative to the number of randomized subjects will be calculated, by formulation and dosing regimen, overall and in each group.

8.2 Adverse Events

All adverse events (AEs) will be coded by system organ class (SOC) and preferred term (PT) (Medical Dictionary for Regulatory Activities [MedDRA] version 20.0). The incidence of the following events in subjects administered IMP using the relevant formulation and dosing regimen will be summarized for all events, by SOC, and by PT.

- Treatment-emergent AEs (TEAEs)
- TEAEs by severity
- TEAEs with an outcome of death
- Serious TEAEs

AEs that emerge after IMP administration in Periods 1 and 2 up to predose in the next period will be regarded as TEAEs in Periods 1 and 2, respectively. AEs that emerge after IMP administration in Period 3 will be regarded as TEAEs in Period 3. If there are multiple occurrences of the same event in the same period in the same subject, the event with the highest severity will be selected. The above summaries will also be prepared for TEAEs potentially causally related to the IMP.

8.3 Clinical Laboratory Data

For each parameter (excluding qualitative urine tests), descriptive statistics of measurements and changes from baseline at each time point will be calculated. A shift table summarizing the test results at each time point classified into “within normal” “below the lower limit of normal,” or “above the upper limit of normal” (using the institutional reference ranges) with comparison to baseline will be created.

For qualitative urine tests, a shift table comparing results to baseline by time point will be created.

8.4 Vital Sign

For each parameter, descriptive statistics of measurements and changes from baseline at each time point will be calculated.

8.5 Physical Examination

For each parameter, a shift table summarizing the findings at each time point compared to baseline will be created.

8.6 **Electrocardiogram Data**

For each 12-lead electrocardiogram (ECG) parameter, descriptive statistics of measurements and changes from baseline at each time point will be calculated. A shift table of ECG findings at each time point compared to baseline assessments will be created. For corrected QT intervals (QTcF and QTcB), the number and percentage of subjects meeting the following conditions will be calculated.

- Subjects with measurements “> 0.450 seconds,” “> 0.480 seconds,” and “> 0.500 seconds”
- Subjects with changes from baseline “> 0.030 seconds” and “> 0.060 seconds”

8.7 **Body Weight**

Descriptive statistics of measurements and changes from baseline at each time point will be calculated.

9 **Pharmacokinetic Analysis**

The following analyses will be performed for the bioequivalence analysis set per cohort. Sensitivity analysis of the primary variable will be performed on subjects for whom evaluable AUC_t and C_{max} values were obtained in Periods 1, 2, or 3.

9.1 **Statistical Analysis of Primary Variables**

- 1) For the AUC_t and C_{max} of tolvaptan, data will be log-transformed and analysis of variance (ANOVA) will be performed using group (group receiving conventional tablet first, group receiving OD tablet without water first, and group receiving tolvaptan OD tablet with water first), formulation and dosing regimen, subjects within group, and administration period (Period 1, Period 2, and Period 3) as factors. The analysis will use natural logarithms.
- 2) For the AUC_t and C_{max} of tolvaptan, the 90% confidence intervals of the ratio of the geometric mean values for the 2 formulations (OD tablet without water vs conventional tablet and OD tablet with water vs conventional tablet) will be calculated. Bioequivalence between the formulations and between the dosing regimens is to be demonstrated when the 90% confidence intervals fall inside the range of $\ln(0.8)$ to $\ln(1.25)$. Bioequivalence between the OD tablet and conventional tablet is to be established when the bioequivalence criteria are met between the OD tablet administered without water and conventional tablet and also between the OD tablet administered with water and conventional tablet. When an add-on subject study is conducted, bioequivalence is to be assessed in the same manner with the pooled data of both the main study and add-on subject study, using the study as a variation factor.

- 3) When there are discontinued subjects or unevaluable data, a sensitivity analysis will be performed. Log-transformed AUC_t and C_{max} values will be analyzed with a linear mixed-effects model, using group, administration period, and formulation and dosing regimen as fixed effects and subjects within group as a random effect, and the difference between formulations (OD tablet without water – conventional tablet and OD tablet with water – conventional tablet) and corresponding 90% confidence intervals will be calculated.

